13.5. Treatment Comparisons

13.5.1. Primary Comparisons of Interest

No formal hypothesis testing will be performed. Safety, PK, PD markers, and efficacy summaries will be provided by initial dose cohort in Part 1 and by expansion cohort in Part 2.

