- Selected dose escalation cohorts may enroll additional subjects in order to further assess safety, PK and/or PD. The frequency and schedule of dosing may be adjusted based on emerging safety, PK and PD data e.g., a recovery period may be incorporated into the dosing. Additional, intermediate dose levels may also be explored.

- Subjects will receive GSK2857916 treatment until disease progression, unacceptable toxicity, withdrawal of consent, or until they have reached the end of the treatment period, which has been pre-specified as 16 cycles (48 weeks) for Schedule 1 (GSK2857916 given once every three weeks; 1 cycle = 21 days).

3.3.1.2. Description of N-CRM for Schedule 1

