3.3.1.2.1. Planned Dose Levels

Prior to the start of the study, projected dose levels on Schedule 1 (in mg/kg) are 0.03, 0.06, 0.12, 0.24, 0.48, 0.96, 1.92, 2.8, 3.6, and 4.5 mg/kg; actual dose levels will be determined by N-CRM (Neuenschwander-Continuous Reassessment Method). Additional doses and schedules may be explored based on emerging safety, PK, and PD data. The maximum dose to be administered in this trial will not exceed 5 mg/kg.

Description of the New Continuous Reassessment Method: After each cohort, a dosing recommendation for the next cohort will be made using the N-CRM [Neuenschwander, 2008]. All available data, including safety, PK and PD data from current and prior cohorts will be reviewed at the dose escalation meeting (see Section 12.1). Although the N-CRM will be used to recommend the next dosing level, clinical judgment by the Medical Monitor and internal dose-escalation committee in consultation with the investigators can halt enrolment into lower dose cohorts as deemed appropriate at any time during the trial.

The N-CRM design is a type of Bayesian adaptive dose escalation scheme that assumes a two-parameter logistic model for the toxicity rate based on dose. It is a modified version of the original Continuous Reassessment Method [O'Quigley, 1990]. A CRM-based design uses a statistical model for dose and toxicity, and is expected to locate the MTD efficiently while minimizing the number of subjects exposed to pharmacologically inactive dose levels.

The method is fully adaptive and makes use of all the DLT information available at the time of each dose assignment. In contrast, the 3+3 method only uses information from one dosing cohort at a time.

At the time of each dose escalation decision, the Fixed and Adaptive Clinical Trial Simulator (FACTS) will be used to obtain, for each potential dose, the posterior probabilities that the DLT rate for that dose lies in each of four toxicity intervals (under dosing, target dose range, excessive toxicity, and unacceptable toxicity). The four DLT toxicity intervals are defined as follows:

- [0%, 16%) Underdosing
- [16%, 33%) Target toxicity
- [33%, 60%) Excessive toxicity

- [60%, 100%) Unacceptable toxicity

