3.5. Intra-Subject Dose Escalation

For the subjects enrolled in Part 1, intra-subject dose escalations may be considered on a case-by-case basis, provided that the subject completed at least 2 cycles at originally assigned dose, still fulfils eligibility criteria, has tolerated treatment well, and did not experience Grade 3 or higher toxicity. A subject's dose may be increased to that of a completed cohort that has not exceeded the MTD. Approval must be obtained from a GSK Medical Monitor. Dose-escalation decisions will be documented on a Dose Escalation/De-escalation Decision Form (see SPM).

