19. Collect cytokines at predose (within 30 minutes prior to SOI) and EOI (± 5 min) (even when infusion is interrupted or halted) to assess allergic reaction)
20. All ADA samples will be collected prior to each infusion
21. PK samples to be taken (in all subjects) for both GSK2857916 and cys-mcMMAF measurement: C1D1 at pre-dose (within 30 minutes prior to SOI), 0.5 h after the start of the infusion (SOI) (± 5 min), at the end of infusion (EOI) just before EOI, 1 h after EOI, 3 h after EOI (± 5 min), 8 h after EOI (± 15 min), 24h after EOI (± 1 h) (Day 2); C1D8 1 sample; C1D15 1 sample; C2D1, at pre-dose (within 30 minutes prior to SOI) and at the EOI (just before EOI); C3D1 at pre-dose (within 30 minutes prior to SOI) and at the EOI (just before EOI).
22. Collect 1 PK sample at each subject's final visit.
23. Pre-specified amounts of urine will be collected for PK analysis from the 24 hour urine collection at Screening, C2D1, C4D1, C7D1, C10D1, C13D1, and C16D1. Refer to Section 7.4.2 for details.
24. Study drug administration ± 3 day window only
25. Prophylaxis with prednisolone phosphate 1% or dexamethasone 0.1% 1 drop QID x 4 days starting 1 day prior to treatment
26. Record subject's survival status and whether subsequent treatment for disease was given. Subject does not need to come in for visit.

Abbreviations:

ADA = Antibody Drug Antibody; ALP = alkaline phosphatase; BCVA = best corrected visual acuity; BNP = B-type natriuretic peptide; C1D1 = Cycle 1 Day 1, etc.; cfDNA = Circulating free DNA; CK = creatinine kinase; CRP = C-reactive protein; EM = extramedullary; EOI = End of Infusion; FLC = free light chain; PD = Pharmacodynamics; PK = Pharmacokinetics; QID = 4 times a day; SOI = start of infusion; SPEP = serum protein electrophoresis; UPEP = urine protein electrophoresis

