In Part 2 of the study, plasma GSK2857916 concentration-time data together with data from part 1 will be analysed using a population approach. A nonlinear mixed effects model will be used to determine population pharmacokinetic parameters and identify relevant covariates (e.g., age, weight, or disease related covariates). PK parameters will be listed and summarized descriptively (mean, standard deviation, median, minimum, maximum, geometric mean, and the standard deviation, CV% and 95% confidence interval of log-transformed parameters) by dose cohort and schedule in Part 1 and Part 2. To assess the extent of accumulation following GSK2857916 repeat dosing, the observed accumulation ratio (R_o) for both GSK2857916 (intact and total) and cys-mcMMAF will be determined as C_{max} and C_{trough} at steady-state to C_{max} and C_{trough} after the first dose, respectively.

Raw urine Concentrations

Urine concentrations of cys-mcMMAF (part 1 only) will be listed and summarised by GSK2857916 dose, schedule and nominal time range. Plots may also be produced if deemed necessary.

Derived Urine Pharmacokinetic Parameters

If data permits, the following pharmacokinetic parameters will be determined for each GSK2857916 dose, each schedule and for each subject (Part 1 only):

Urinary recovery of unchanged cys-mcMMAF within the 24 h period collection ($A_e(0-24)$) will be calculated. It will be calculated as the product of the concentration in urine and the urine weight, thus assuming a urine density of 1 g/mL.

Fraction of total cys-mcMMAF dose excreted (F_e) in the 24-h interval will be estimated as $A_e(0-24)/(\text{cys-mcMMAF})\text{Dose}$, in the Schedule 1 only (i.e. every 3weeks).

Derived cys-mcMMAF urine pharmacokinetic parameters will be listed and summarised by GSK2857916 dose and schedule.

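### Part 1 results are grouped only by initial dose cohort although subjects may be escalated after two cycles, so later events and responses are credited to a lower starting dose

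*Protocol*

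**What the plan says.** Protocol Section 13.5.1 fixes the Part 1 grouping: "Safety, PK, PD markers, and efficacy summaries will be provided by initial dose cohort in Part 1". Sections 13.5.1.1 and 13.5.2 repeat the grouping by dose cohort.

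Section 3.5 says that "intra-subject dose escalations may be considered on a case-by-case basis, provided that the subject completed at least 2 cycles at originally assigned dose". On the ceiling it says: "A subject's dose may be increased to that of a completed cohort that has not exceeded the MTD". The move is not limited to one dose level.

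Section 13.7 analyses all data up to completion or withdrawal, whatever the length of treatment. Section 13.7.2 adds a worst-case summary over every on-treatment time point. No section cuts a subject's data at escalation, assigns an event to the dose in effect at onset, or asks for escalated subjects to be flagged.

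For Part 1 plasma PK on Schedule 1, footnote 21 of Section 7.1.1.1 schedules repeat-dose samples on "C2D1, at pre-dose (within 30 minutes prior to SOI) and at the EOI (just before EOI); C3D1 at pre-dose" and again at the end of that infusion. Cycle 3 Day 1 (C3D1) is the last serial PK day. Section 13.7.3.1 then compares later with first-dose values: "To assess the extent of accumulation following GSK2857916 repeat dosing, the observed accumulation ratio" is to be derived from Cmax and Ctrough.

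**The concern.** The initial cohort describes what a subject received only until the first escalation. After that, the Part 1 tables attach high-dose experience to a low-dose label. A corneal event or a partial response at a later cycle appears in the row of a dose the subject had already left. Toxicity and activity then both look higher than they are at low doses, and the dose relationships look flatter.

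This bears on dose selection. Section 3.4 allows a dose below the MTD to be taken into Part 2 when, among other conditions, there are emerging signs of clinical activity at that dose. A response credited to the wrong dose feeds that judgement. The run-in cohorts of Section 3.3.1.1 have one subject each, so a single misplaced event is the cohort's whole result.

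**Working it through.** The plan states no figure to reproduce. The check sets the rules side by side and adds simple arithmetic.

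**1. Share of treatment under the wrong label.** Section 3.5 requires two cycles before escalation. Section 3.3.1.1 gives the treatment period, "which has been pre-specified as 16 cycles (48 weeks) for Schedule 1", and 16 × 21 days = 336 days = 48 weeks. If escalation occurs at Cycle 3 and the subject is treated for n cycles, the share after escalation is (n − 2)/n:
- n = 4: 2/4 = 50%
- n = 8: 6/8 = 75%
- n = 16: 14/16 = 87.5%

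**2. Which doses can be reached, and when.** The projected levels of Section 3.3.1.2.1 start at 0.03 mg/kg and continue "0.06, 0.12, 0.24, 0.48, 0.96, 1.92, 2.8, 3.6, and 4.5 mg/kg". Cohorts open one after another, each after the previous 21-day window, with at most a doubling (Sections 3.3.1.1, 3.3.1.2.1 and 12.1). Only a completed cohort's dose is available. Take a run-in subject starting at 0.24 mg/kg on day 0, with no time lost between cohorts:
- 0.48 mg/kg completes on day 42, which is this subject's C3D1
- 0.96 mg/kg completes on day 63 (Cycle 4 Day 1)
- 1.92 mg/kg completes on day 84 (Cycle 5 Day 1)

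At C3D1 the largest possible dose ratio is therefore 0.48/0.24 = 2.

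**3. Cumulative dose received against the dose implied by the label.** For one escalation at Cycle 3 from d0 to d1, the ratio is (2·d0 + (n − 2)·d1)/(n·d0):
- 0.48 to 0.96 mg/kg: 1.5 (n = 4), 1.75 (n = 8), 1.875 (n = 16)
- 2.8 to 3.6 mg/kg: 1.14, 1.21, 1.25

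A later and larger move is possible. From 0.24 to 1.92 mg/kg at Cycle 5, with all 16 cycles given, 12/16 = 75% of cycles are at eight times the labelled dose. The ratio is (4 × 0.24 + 12 × 1.92)/(16 × 0.24) = 24.00/3.84 = 6.25.

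**4. Plasma PK, Schedule 1.** Scheduled samples are 7 (Cycle 1 Day 1 to Day 2) + 1 (Day 8) + 1 (Day 15) + 2 (Cycle 2 Day 1) + 2 (C3D1) + 1 (final visit) = 14. Only 2 of the 14 can follow an escalated dose: the C3D1 end-of-infusion sample and the final-visit sample. All single-dose parameters come from Cycle 1. The C3D1 pre-dose Ctrough still reflects the starting dose. If the dose doubles at C3D1 and Cmax is proportional to dose, the ratio of that Cmax to the first-dose Cmax is about 2 with no accumulation at all.

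**5. What lies outside the problem.** DLTs are counted in the first 21 or 28 days, before any escalation is possible, so the N-CRM and the MTD are untouched. Section 3.5 applies to Part 1 only, so the Part 2 futility rule is untouched.

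**The case against.** The strongest defence is that grouping by initial cohort is a common and sound choice. Section 3.5 confines escalation to subjects who completed two cycles, tolerated treatment well, had no Grade 3 or higher toxicity and still meet eligibility. Moving their later data to the higher dose fills the high-dose rows with selected tolerators, and a late event may reflect cumulative exposure rather than the current dose. This stands. It is a reason to keep the table, but not to have it as the only display.

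A second defence is that details are left to the analysis plan, which may add a companion display, and that Section 13.7.1 speaks of response by dose level. That is possible. But the grouping itself is fixed in the protocol, and Section 13.7.1 does not say whether the dose is initial or actual.

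On PK, Section 13.7.3.1 derives parameters for each dose and defines the accumulation ratio at steady state, and the power model of Section 13.7.3.2 does not say that its dose is the initial one. This narrows the PK point to the end-of-infusion value on the last serial sampling day.

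Two stronger readings are tempting and not supported:
- A reader might infer an eight-fold Cmax distortion at C3D1, for instance from 0.24 to 1.92 mg/kg. The sequence of cohorts rules this out, except for a subject added late to a low cohort, which Section 3.3.1.1 permits.
- A reader might infer that the recommended dose rests on these tables. Section 3.4 draws on all safety, PK and PD data, including receptor occupancy and exposure relationships. Investigators review the data of all subjects at regular meetings (Section 12.1), and each escalation is documented on a form (Section 3.5).

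**Conclusion.** The point holds in limited form. As written, the only stated Part 1 grouping credits adverse events, worst-case laboratory values and responses after escalation to the lower starting dose. For a subject escalated at Cycle 3, this covers 50% to 87.5% of cycles, depending on whether 4 or 16 are given. The PK effect is confined to the C3D1 end-of-infusion Cmax and what is derived from it, with a dose ratio of at most about 2 for sequentially enrolled run-in subjects.

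The size rests on three assumptions: a single escalation, no time lost between cohorts, and, for the PK figure, Cmax proportional to dose. Escalation is case by case, so the number of subjects affected is unknown and could be zero. The change is worth making because it is cheap and because very small cohorts leave no room for misplaced events. It does not call the MTD, single-dose PK or the Part 2 test into question.

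**What to change.** Leave the escalation rule in Section 3.5 as it is, and keep the initial-dose-cohort table as the main Part 1 display. Add to Sections 13.5.1 and 13.7:
- a companion Part 1 display of adverse events, worst-case laboratory values and responses by dose in effect at onset, or with each subject's data cut at the first escalation
- a flag and a listing of all escalated subjects, with dates and doses
- the accumulation ratio and repeat-dose Cmax by cohort computed only in subjects whose dose is unchanged since Cycle 1 Day 1
- the actual dose, not the initial dose, in the repeat-dose power model

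State that the companion display is supportive, because post-escalation data come from subjects selected for tolerating treatment and may reflect cumulative exposure.

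The cost is a few sentences and one derived variable. Administration is already recorded in the eCRF (Section 4.4), and escalations on the decision form (Section 3.5). No new data are needed.

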13.5.1.1. Primary Comparison of Interest

All available data, including adverse events, changes in laboratory values and other safety parameters will be evaluated for each dose cohort in Part 1 and for each expansion cohort in Part 2.

13.5.2. Other Comparisons of Interest

Pharmacokinetic: PK parameters will be evaluated and summarized for each dose cohort in Part 1 and in Part 2.

Pharmacodynamic markers: Changes from baseline in PD markers will be evaluated and summarized for each dose cohort in Part 1 and for Part 2.

Clinical anti-cancer activity: The number of Overall Responders (PR, VGPR, CR or sCR) for each dose cohort in Part 1 and for each expansion cohort in Part 2 will be listed and summarized if data warrant. Clinical Benefit Rate (CBR), as defined in [Appendix 1](#), may also be explored. The results from the independently reviewed scans may also be reported if data are available.

13.6. Interim Analysis

13.6.1. Part 1

While no formal interim analysis is planned for Part 1, safety, pharmacokinetic and pharmacodynamic marker data will be examined on an ongoing basis to support dose escalation decisions. Prior to determining the GSK2857916 dose for the next cohort enrolled, exploratory analysis will be conducted to assess the relationship of GSK2857916 dose levels with safety, PK and PD parameters using all data from available cohorts. For more details of the dose escalation procedure, see Section 3.3.

13.6.2. Part 2

The methodology utilized is based on the predictive probability of success if enrollment continues to 40 subjects [Lee, 2008]. The predictive probability design is similar to a Green-Dahlberg design in that it allows for early stopping for futility. The differences are that the predictive probability design allows for evaluation of stopping rules as often as after each subject, rather than at only two stages. While the two designs have similar type I and type II error rates, the probability of early termination is greater with the predictive probability design. In this particular study, we will stop only for futility and evaluate the stopping rules once approximately 15, 22, and 30 subjects are evaluable (though additional futility looks are also controlled for if necessary). A subject is considered evaluable if they are in the all treated population and have had at least two post baseline disease assessments.

For the MM expansion cohort, response data will be reviewed once approximately 15, 22, and 30 subjects are evaluable and the number of overall responses (PR, VGPR, CR, and sCR) observed will be compared with the stopping rules provided in Table 17 below.

Table 17 Futility Stopping Region

Number of Evaluable Subjects	Number of Overall Responses												
	0	1	2	3	4	5	6	7	8	9	10	11	>11
15	Shaded	Shaded	Shaded										
16	Shaded	Shaded	Shaded										
17	Shaded	Shaded	Shaded										
18	Shaded	Shaded	Shaded	Shaded									
19	Shaded	Shaded	Shaded	Shaded									
20	Shaded	Shaded	Shaded	Shaded									
21	Shaded	Shaded	Shaded	Shaded									
22	Shaded	Shaded	Shaded	Shaded	Shaded								
23	Shaded	Shaded	Shaded	Shaded	Shaded								
24	Shaded	Shaded	Shaded	Shaded	Shaded								
25	Shaded	Shaded	Shaded	Shaded	Shaded	Shaded							
26	Shaded	Shaded	Shaded	Shaded	Shaded	Shaded							
27	Shaded	Shaded	Shaded	Shaded	Shaded	Shaded							
28	Shaded	Shaded	Shaded	Shaded	Shaded	Shaded							
29	Shaded	Shaded	Shaded	Shaded	Shaded	Shaded	Shaded						
30	Shaded	Shaded	Shaded	Shaded	Shaded	Shaded	Shaded						
31	Shaded	Shaded	Shaded	Shaded	Shaded	Shaded	Shaded						
32	Shaded	Shaded	Shaded	Shaded	Shaded	Shaded	Shaded	Shaded					
33	Shaded	Shaded	Shaded	Shaded	Shaded	Shaded	Shaded	Shaded	Shaded				
34	Shaded	Shaded	Shaded	Shaded	Shaded	Shaded	Shaded	Shaded	Shaded	Shaded			
35	Shaded	Shaded	Shaded	Shaded	Shaded	Shaded	Shaded	Shaded	Shaded	Shaded			
36	Shaded	Shaded	Shaded	Shaded	Shaded	Shaded	Shaded	Shaded	Shaded	Shaded			
37	Shaded	Shaded	Shaded	Shaded	Shaded	Shaded	Shaded	Shaded	Shaded	Shaded	Shaded		
38	Shaded	Shaded	Shaded	Shaded	Shaded	Shaded	Shaded	Shaded	Shaded	Shaded	Shaded		
39	Shaded	Shaded	Shaded	Shaded	Shaded	Shaded	Shaded	Shaded	Shaded	Shaded	Shaded	Shaded	
40	Shaded	Shaded	Shaded	Shaded	Shaded	Shaded	Shaded	Shaded	Shaded	Shaded	Shaded	Shaded	Shaded

Note: The shaded regions are the specific regions for stopping the study for futility. For instance, if there are 4-5 or fewer responses in 25 subjects, then the predictive probability for success will be less than the futility criterion, 5.0%, and the study will be stopped.

In addition to the considering the recommendations of the futility analyses, final decisions on stopping enrolment in the MM cohort will depend on the totality of the data collected. Examples of consideration of the totality of the data include, further investigation of the clinical activity of subgroups of subjects based on their BCMA expression levels and evaluation of the quality of responses (including sCR, CR and Clinical Benefit Rate, as defined in [Appendix 1](#)). Should the recommendation to stop for futility be disregarded in favor of a decision to continue the trial based on the totality of the data, the overall type I error rate of the expansion phase will be inflated.

No interim analyses will be performed on the BCMA+ lymphomas cohort; though consideration would be given to closing the cohort should the enrollment be stopped in the MM cohort.

If necessary, a subject may be replaced if they are deemed to be Lost to Follow-Up (LTFU) or they have withdrawn due to a toxicity deemed to not have been related to GSK2857916.

Subjects will not be replaced when they discontinue the study due to: Progression (symptomatic or otherwise), toxicity related to GSK2857916, or lack of efficacy.

Other administrative interim analyses may be performed if needed.

Final analysis of MM population may be performed separately, before the NHL cohort completes the study.

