13.2.2. Part 2: Expansion Cohort

Dose escalation will be used to establish the RP2 dose for GSK2857916. Once the RP2 dose is confirmed, at least 15 and up to 40 subjects in total will be enrolled into the MM cohort using decision rules defined in [Table 17](#). The sample size and stopping rules are based on the methodology of Lee et al. [[Lee, 2008](#)]. The assumptions underlying the design are detailed below.

The null hypothesis is:

$$H_0: p \leq 20\%$$

The alternative hypothesis is:

$$H_A: p \geq 40\%$$

For the MM expansion cohort, starting with 15 subjects and allowing for a maximum sample size of 40, this design will have a type I error rate (α) of 0.075 and 89.8% power. The trial is not designed to stop early for efficacy, but is designed to stop early for futility if the predictive probability of success is less than 5%. The type I error rate, power, and predictive probability of success to stop early for futility were derived from explicitly stating the minimum and maximum sample size, allowing for the futility stopping rate to range from 5% to 20% within the predictive probability design software, and selection of the optimizing criterion as the maximization of power under the alternative hypothesis. The Bayesian prior probability used in determining the design was Beta (0.25, 0.75), a distribution with a mean response rate of 25%. Under the null hypothesis, if the true response rate is 20%, the expected sample size of the design is 23.4 subjects and probability of early termination (PET) is 88.9%. Under the alternative hypothesis, if the true response rate is 40%, the expected sample size of the design is 38.6 subjects and probability of early termination (PET) is 8.5%.

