13.4.1. Analysis Populations

The ‘All Treated’ population is defined as all eligible subjects who receive at least 1 dose of study treatment. An incorrect treatment schedule or drug administration or an early termination of treatment will not result in exclusion of subjects from this population. Subjects with major deviations from the eligibility criteria affecting safety or from the treatment schedule at the DLT evaluation period (1 cycle: 21 days for once every 3 weeks schedule or 28 days for once weekly schedule) for reasons other than toxicity may be presented in separate tables/listings.

The ‘All Treated’ population will further be classified in the following sub-populations.

- Part 1: all Part 1 subjects of All Treated population. Note, subjects in Part 1 are exclusively multiple myeloma patients.
- Part 2 MM: all Part 2 MM subjects of All Treated population
- All Treated MM: comprise of subjects in Part 1 and Part 2 MM.
- Part 2 NHL: all Part 2 lymphoma subjects of All Treated population.

The ‘**DLT Evaluable**’ population in Part 1 enables an appropriate evaluation of study DLTs. It is defined as those subjects fulfilling the ‘All Treated’ population criteria, and having met the following adequate exposure criteria:

- For Schedule 1 (once every 3 weeks dosing) subjects received a complete infusion in cycle 1.
- For Schedule 2 (once weekly dosing for 3 consecutive weeks, 1 week rest) subjects receive three infusions, two of which must be complete infusions, in cycle 1. (as increases up to $\leq 30\%$ are implemented between cohorts, less than 2 complete infusions would result in a total dose closer to the previous dose investigated).

Any subject in the “All Treated” population who experiences a DLT, as defined in Section 3.3.3 will also be included in the DLT evaluable population regardless of exposure.

The ‘**Evaluable (MM)**’ population is a subset of the ‘All Treated’ population, who were initially treated at RP2D in the expansion cohort and have at least two post-baseline disease assessments or they have progressed or died or permanently discontinued treatment. This population will be used for the futility analysis of the MM expansion cohort.

The ‘**Pharmacokinetic (PK) Population**’ is defined as those subjects in the “All Treated” population from whom at least one PK sample was obtained, analyzed, and was measurable.

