13.7.7. Clinical Activity Analyses

Overall Response Rate (ORR) is one of the secondary endpoints to measure clinical activity of this study.

For multiple myeloma, ORR is defined as the percentage of subjects with a confirmed PR or better (i.e. PR, VGPR, CR and sCR), according to the IMWG Panel I ([Appendix 1](#)), as assessed by the investigator. In addition, Clinical Benefit rate (CBR) is defined as the percentage of subjects with a confirmed MR or better (i.e. MR, PR, VGPR, CR and sCR), according to the IMWG Panel I ([Appendix 1](#)), as assessed by the investigator.

The number and percentage of subjects in the following response categories will be presented sCR (stringent complete response), (complete response) CR, (very good partial response) VGPR, (partial response) PR, (minimal response) MR, stable disease (SD), progressive disease (PD), and not evaluable (NE)

sCR+CR+VGPR+PR for overall response (ORR)

sCR+CR+VGPR+PR+MR for Clinical Benefit rate (CBR)

The corresponding exact 95% CI for ORR and Clinical Benefit Rate (CBR) will also be provided. Subjects with unknown or missing response will be treated as non-responders, i.e., these subjects will be included in the denominator when calculating percentages of response.

For lymphoma, ORR is defined as the percentage of subjects with confirmed CR, or PR, as described in the Revised Response Criteria for Malignant Lymphoma ([Appendix 2](#)). ORR for lymphomas will be summarized in a similar way as multiple myeloma. The corresponding exact 95% CI for ORR will also be provided.

Other exploratory time-to-event (TTE) endpoints related to clinical activity for Part 2 (MM) of this study are TTP, DOR, TTR, and PFS.

Time to disease progression (TTP) is defined as the time from first dose until the earliest date of PD per IMWG, or death due to PD. Determination of dates of TTP event and dates for censoring will be described in the RAP. **Duration of response (DOR)** is defined as the time from first documented evidence of PR or better until disease progression (PD) per IMWG, or death due to PD among subjects who achieve a response

(i.e. confirmed PR or better). Responders without disease progression will be censored at the censoring time point for TTP.

Time to response (TTR) is defined as the time between the date of first dose and the first documented evidence of response (PR or better). Subjects without confirmed response (PR or better) will be censored at the censoring date for TTP.

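### Sections 13.4.1 and 13.6.2 define the evaluable set for the same myeloma futility looks differently; following 13.6.2 drops early failures and makes an inactive drug less likely to be stopped

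*Protocol*

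**What the plan says.** **Section 13.6.2** evaluates the stopping rules at about 15, 22 and 30 evaluable subjects and defines the term on the spot: "A subject is considered evaluable if they are in the all treated population and have had at least two post baseline disease assessments". No exception is made for a subject who fails sooner. Table 17 is indexed by the number of evaluable subjects, and Section 13.1.2 sends the ORR test to the stopping rules of 13.6.2.

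**Section 13.4.1** defines the Evaluable (MM) population as expansion subjects first treated at the recommended dose who "have at least two post-baseline disease assessments or they have progressed or died or permanently discontinued treatment". It then states its purpose: "This population will be used for the futility analysis of the MM expansion cohort".

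**Replacement (13.6.2):** "a subject may be replaced if they are deemed to be Lost to Follow-Up (LTFU) or they have withdrawn due to a toxicity" judged unrelated to the drug. The next sentence rules out replacement after progression, drug-related toxicity or lack of efficacy. Nothing says whether a replaced subject stays in the Table 17 count.

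**Final analysis:** Section 13.7.1 uses the All Treated population, and Section 13.7.7 adds: "Subjects with unknown or missing response will be treated as non-responders".

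**Design figures (13.2.2):** "starting with 15 subjects and allowing for a maximum sample size of 40, this design will have a type I error rate (α) of 0.075", with 89.8% power. Further, "if the true response rate is 20%, the expected sample size of the design is 23.4 subjects" with 88.9% probability of early termination, and "if the true response rate is 40%, the expected sample size of the design is 38.6 subjects" with 8.5%. Enrolment in the cohort is limited to 40.

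**The concern.** Both definitions are current text, serve the same analysis and give different denominators. In the 3-weekly expansion schedule (Section 7.1.2.1), the myeloma laboratory tests are repeated at the start of each cycle from Cycle 2. A second post-baseline assessment therefore falls about six weeks after the first dose. Subjects who die, progress or stop before then are almost all non-responders. Section 13.4.1 counts them as failures; 13.6.2 leaves them out.

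The same responses could then cross a Table 17 boundary under one section and miss it under the other. The error runs one way: removing non-responders raises the interim response rate, so an inactive drug is carried further and more patients are treated with it.

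**Working it through.** **1. Reproduce the stated design.** Inputs from 13.2.2: prior Beta(0.25, 0.75), maximum 40, stop if the predictive probability of success is below 5%, null rate 20%, alternative 40%. With x responses in n subjects,

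PP = P(x + Y ≥ r), Y ~ beta-binomial(40 − n, 0.25 + x, 0.75 + n − x).

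I tried success cut-offs r = 11, 12 and 13 of 40, with a look after every subject from 15 to 39. Only r = 12 reproduces the protocol: type I error 0.0754, power 0.8975, early termination 0.8885 and 0.0849, expected size 23.4 and 38.6. (r = 11 gives type I error 0.141; r = 13 gives 0.038.)

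At the planned looks the boundaries are ≤2/15, ≤4/22 and ≤6/30, as in Table 17. With those three looks only, type I error is 0.080, power 0.908 and early stopping under the null 68.3%.

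**2. Model the loss.** Let d be the share of treated subjects, all non-responders, who fail before a second assessment. The protocol gives no value, so I use 5% to 20%. The response rate among 13.6.2-evaluable subjects is 0.20/(1 − d).

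Hand check at the first look:
- d = 0: P(X ≤ 2 | 15, 0.200) = 0.035 + 0.132 + 0.231 = 0.398
- d = 10%: P(X ≤ 2 | 15, 0.222) = 0.023 + 0.099 + 0.198 = 0.320

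**3. Run the rule within 40 enrolled.** Each treated subject is a responder (probability 0.20), an early loss (d) or an evaluable non-responder (0.80 − d). Looks occur when the evaluable count reaches 15, 22 and 30. Success is at least 12 responders among the 40 treated.

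| d | ORR among evaluable | Stopped early | Mean treated | Type I error |
|---|---|---|---|---|
| 0 | 20.0% | 68.3% | 25.7 | 0.080 |
| 5% | 21.1% | 63.3% | 27.5 | 0.082 |
| 10% | 22.2% | 57.6% | 29.4 | 0.084 |
| 15% | 23.5% | 51% | 31.3 | 0.085 |
| 20% | 25.0% | 42.5% to 43.1% | 33.1 | 0.086 |

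In the last row, the higher figure also counts a crossing that coincides with the 40th enrolment, when nothing is left to stop. The type I error cannot exceed P(X ≥ 12 | 40, 0.20) = 0.0875, its value with no futility stopping at all.

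With looks after every subject, early stopping falls from 88.8% to 80.8%, 72.3%, 62.4% and 51.7%.

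**4. Without the enrolment limit.** If accrual ran until 40 subjects were evaluable, 40/(1 − d) = 42.1, 44.4, 47.1 or 50.0 would have to be treated. The three-look type I error would then be 0.108, 0.147, 0.198 or 0.264.

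**The case against.** **Section 13.4.1 already settles it.** It names the population and gives it this purpose, so the 13.6.2 sentence may be shorthand that was never aligned. That is a fair reading. But 13.6.2 is where the rule is applied, it carries its own explicit definition, and 13.1.2 points the test to it. A team following 13.6.2 would not be misreading it.

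**The early loss may be small.** Two sets of myeloma tests exist by Cycle 3 Day 1, and a note in Appendix 1 asks for two consecutive assessments before relapse or progression is classified. Many early progressors would therefore be evaluable under either section, leaving mainly deaths and discontinuations in the first two cycles. This stands: the size rests on an assumed share.

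**The stakes are limited.** Safety is the primary objective, ORR is secondary, Section 13.5.1 disclaims formal testing, and 13.6.2 lets the totality of the data override the rule. This lowers the severity. It does not justify two denominators for one rule.

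**Stronger readings a reader might infer:**
- *Type I error of 0.11 to 0.26.* Table 17 is indexed by evaluable subjects up to 40, which invites this. It needs 42 to 50 treated subjects, whereas 13.2.2 limits enrolment to 40 and 13.6.2 bars replacement for the main kinds of early failure.
- *An inflated reported ORR.* Only the interim count is affected. The final ORR is on all treated subjects, with missing response as non-response.
- *Replacement removes failures from the count.* The protocol does not say that replaced subjects leave the denominator. It is silent, and that silence is the gap to close.

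**Conclusion.** The inconsistency is real and bears on a decision rule. If 13.6.2 is followed, futility stopping weakens: at a true ORR of 20% with the three planned looks, the chance of stopping early drops from 68% to about 63%, 58%, 51% or 43% for an early loss of 5%, 10%, 15% or 20%. At 10% loss the mean number treated rises by 29.4 − 25.7 = 3.7; at 20%, by 33.1 − 25.7 = 7.4.

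These sizes assume that the share d applies, that every early loss is a non-responder, and that success means 12 or more responders of 40, the cut-off that reproduces the protocol's figures. The direction of the effect does not depend on the value of d. The point does not extend to a material rise in type I error within the enrolment limit, nor to the final ORR.

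**What to change.** In Section 13.6.2:

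1. Replace the evaluability sentence with a reference to the Evaluable (MM) population of Section 13.4.1.
2. State that subjects who progress, die or permanently discontinue before a second assessment, without a confirmed response, count as non-responders in Table 17.
3. State that a replaced subject stays in the Table 17 denominator as a non-responder, in line with Section 13.7.7.

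The first two changes keep the null rate among evaluable subjects at 20%, the condition under which the figures in 13.2.2 hold.

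The cost is wording, plus a somewhat higher chance of crossing the futility boundary than under the 13.6.2 definition. For an active drug that cost is bounded. At a true ORR of 40%, power is 0.908 with the three looks and 0.929 with no futility stopping, so within 40 subjects the looser definition could save at most 0.929 − 0.908 = 0.021.
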